## 6. Endpoints

#### Primary endpoints:

1. Sustained virologic response (no HCV RNA detectable 24 weeks after the end of treatment).

#### Secondary endpoints:

- 1. Early virologic response after 12 weeks of therapy with PegIntron, Rebetol, AdoMet and betaine.
- 2. Cmax and AUC of mRNA induction of IFN stimulated genes over 96 hours after first injection of PegIntron (RNA extracted from whole blood).

## 7. Evaluation, Statistics

## 7.1. Primary Endpoints:

The sustained response rate in this group of patients will be compared to response rates published in other studies (=historical control). In a recent publication from the HALT-C trial, the sustained response rate of a treatment with PegIFN $\alpha$ 2a plus ribavirin of 385 patients that were non-responders or relapser of a previous treatment with IFN $\alpha$  plus Ribavirin was 12% (22).

We have no preliminary data that would allow us to estimate the sustained response rate in previous (peg)IFN $\alpha$  plus ribavirin non-responders when treated with a combination of pegylated IFN $\alpha$ , ribavirin, AdoMet and betaine. We postulate that an improvement of the sustained response rate of 20% or more would be clinically relevant.

In order to detect a difference of 20% with a 5% significance ( $\alpha$ ) and 80% power ( $\beta$ ), we estimate the sample size with the following formula:

$$n = \left[ \frac{z_{\alpha} \sqrt{\pi_0 (1 - \pi_0)} - z_{\beta} \sqrt{\pi_1 (1 - \pi_1)}}{\pi_0 - \pi_1} \right]^2$$

$$\begin{split} \pi_0 &= 0.12 \\ \pi_1 &= 0.32 \\ \alpha &= 0.05 \\ z_\alpha &= 1.96 \text{ (two-tailed)} \\ \beta &= 0.2 \\ z_\beta &= -0.84 \text{ (one-tailed)} \end{split}$$

$$n = \left[\frac{1.96\sqrt{0.12(1-0.12)} - (-0.84)\sqrt{0.32(1-0.32)}}{0.12 - 0.32}\right]^2 = \left[\frac{1.96\sqrt{0.12*0.88} + 0.84\sqrt{0.32*0.68}}{-0.2}\right]^2 = \left[\frac{1.96\sqrt{0.1056} + 0.84\sqrt{0.2176}}{-0.2}\right]^2 = 26.4$$

For this non-responder group, the sample size N = 26.4

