## 4. Experimental Design

Prospective, randomized, open label pilot study to test the efficacy and safety of a combination treatment with PegIntron, Rebetol, AdoMet and betaine in **non-responders** 

of previous combinations therapy with (peg)IFNα and Ribavirin.

Half of the patients (Group A) will be treated during the first week with AdoMet and Betaine, followed by a combination treatment of PegIntron, Rebetol, AdoMet and Betaine.

The other half of the patients (Group B) will be treated during the first 1 week with PegIntron and Rebetol, followed by a combination treatment of PegIntron, Rebetol, AdoMet and Betaine. (This randomized assignment to groups A or B will allow to test the usefulness of the surrogate marker ISG induction for predicting treatment response). The randomization will be done in two separate groups for genotype 1 and 4 and for genotypes 2 and 3, respectively. In each group, a list with a randomized sequence of A's and B's in blocks of 10 will be used to assign the patients into groups A or B.

The study will be performed at the University Hospital Basel.

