#### **Duration of treatment**: will depend on HCV-genotype

- 24 weeks for genotypes 2 and 3
- 48 weeks for genotypes 1, 4 and 5

For patients, who do not show an adequate response at week 12 (adequate response at week 12 = drop of HCV RNA of at least 2log or HCV RNA-negativity), treatment can be stopped and the patient enters follow up phase.

**Duration of study:** Will include the treatment period (24 or 48 weeks) as well as the follow-up period of 24 weeks (totally: 48 or 72 weeks)

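### SVR pooled over genotypes is compared with a single published 12% of unstated genotype mix, so the error rate and power of the primary comparison can shift with the mix enrolled

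*Protocol*

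**What the plan says.** Section 6 of the protocol defines one primary endpoint, sustained virologic response (SVR) 24 weeks after treatment ends, without distinguishing genotypes. Section 7.1 sets the comparison: "The sustained response rate in this group of patients will be compared to response rates published in other studies". The one study it then cites supplies the 12%, from "385 patients that were non-responders or relapser of a previous treatment". The same 12% is the null rate in the sample-size formula. The target is stated as "We postulate that an improvement of the sustained response rate of 20% or more would be clinically relevant", that is, 32%.

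Elsewhere the protocol treats genotype as something that matters. Treatment duration in Section 10.2 is "24 weeks for genotypes 2 and 3" and 48 weeks for genotypes 1, 4 and 5. Section 4, repeated in Section 8, says: "The randomization will be done in two separate groups for genotype 1 and 4 and for genotypes 2 and 3, respectively". Section 5 plans 30 patients and has no genotype criterion or cap. Groups A and B both go on to the full four-drug combination after the first week (Sections 4 and 10.3).

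**The concern.** The primary question has no concurrent control. The comparison is sound only if 12% is the SVR that these 30 patients would have had without AdoMet and betaine. That rate depends on case mix, and the protocol's own design choices mark genotype as a relevant part of it. Stratified randomisation does not help, because it balances A against B and the primary comparison is of A and B together with an outside figure.

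If genotype 2/3 patients have a higher retreatment SVR and make up a larger share here than in the source, the true no-effect rate lies above 12%, and a surplus of responders could be read as a drug effect. If their share is smaller, a real effect becomes harder to show. Section 7.1 gives neither the source's genotype mix nor any adjustment, so a reader cannot tell which case applies.

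**Working it through.** **1. The plan's own figure.** Inputs from Section 7.1: null 0.12, alternative 0.32, z = 1.96 (two-sided 5%) and 0.84 (80% power).

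n = [(1.96·√0.1056 + 0.84·√0.2176) / 0.20]² = [(0.6369 + 0.3918) / 0.20]² = 26.46

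The protocol prints 26.4 and plans 30. The arithmetic is sound for those inputs.

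**2. A decision rule.** The protocol states none. I use the exact binomial rule with an upper tail of at most 2.5%, which matches a two-sided 5% test. For N = 30 and rate 0.12:

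- P(X ≥ 7) = 6.1%
- P(X ≥ 8) = 2.2%

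The rule is therefore at least 8 of 30. Its power at 32% is 79.2%.

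**3. No drug effect, mixed genotypes.** Let m of the 30 patients be genotype 2/3 with no-effect SVR b, and the other 30 − m have no-effect SVR a. The total count is the sum of Bin(30 − m, a) and Bin(m, b). Its expected rate is [a(30 − m) + b·m]/30, and the false-positive risk is the exact probability that the sum is 8 or more. The documents give neither a nor b, so the pairs are assumptions.

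| Assumed a / b | m = 6 | m = 10 | m = 15 |
|---|---|---|---|
| 12% / 12% | 2.2% | 2.2% | 2.2% |
| 8% / 20% | 0.9% | 2.0% | 4.7% |
| 8% / 30% | 2.2% | 6.8% | 18.8% |
| 10% / 30% | 4.5% | 10.6% | 23.3% |

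For 10%/30% the no-effect rates are 14.0%, 16.7% and 20.0%; for example, (0.10·20 + 0.30·10)/30 = 16.7%.

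Each unequal pair is compatible with a 12% source at some genotype 2/3 share s, where a(1 − s) + b·s = 0.12:

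- 8%/20%: s = 0.04/0.12 = 33%
- 8%/30%: s = 0.04/0.22 = 18%
- 10%/30%: s = 0.02/0.20 = 10%

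When the enrolled share equals s, the risk stays near nominal (2.0% for 10%/30% at m = 3, and 2.0% for 8%/20% at m = 10). The excess comes from the difference between the two mixes.

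**4. The opposite mix.** With no genotype 2/3 patients and an assumed no-effect rate of 8%, a true gain of 20 points gives 28%. Then P(X ≥ 8) = 63%, against the 80% planned.

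**5. The relapser offset.** The benchmark includes relapsers; the trial takes non-responders only, and Section 2 puts their retreatment response below 10%. A uniform no-effect rate of 10% gives P(X ≥ 8) = 0.8%. Combining both features, assume a source rate of 10% for non-responders, with 10% of them genotype 2/3 at 30%. Then a = (0.10 − 0.03)/0.90 = 7.8%, and the risk at m = 3, 6, 10 and 15 is 0.6, 2.0, 6.5 and 18%. The offset reduces the inflation and can reverse it at low shares, but does not remove it at high ones.

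**The case against.** The strongest reply is that the size rests entirely on assumed rates: no genotype-specific SVR is given, and the source's mix is unknown. With a modest gap (8%/20%) the risk is at or below nominal up to 10 genotype 2/3 patients and only 4.7% at 15. The relapser mismatch pulls the other way. Section 7.1 refers to published rates in the plural and states no test, and Section 4 calls the trial a pilot. All of this stands, and it limits the point to what can happen.

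Three stronger readings are tempting and not supported.

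- A reader might take a large gap such as 12%/50%, which gives 20.5, 47.1 and 78.1% at 6, 10 and 15 patients. That pair fits a 12% source only if the source held no genotype 2/3 patients, and it implies no-effect rates of 24.7% and 31% at 10 and 15 patients, far from the below-10% of Section 2.
- A reader might infer from the two similar lists in Appendix 4 that half the sample will be genotype 2/3. The lists hold about 20 places each for 30 patients. That is capacity, and says nothing about the expected mix.
- A reader might treat 8 of 30 as the protocol's own criterion. It is my construction from the stated 12%, 5% and N.

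The objection does not dispose of the point. A separate analysis plan could add a stratum breakdown, but the protocol itself fixes 12% as the null and derives N from it, and a different null changes both. The plural wording leaves the choice of comparator open rather than settling it. Pilot or not, Section 3 states a superiority hypothesis and Section 7.1 a 5% significance level.

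**Conclusion.** The point holds in conditional form. Section 7.1 compares a pooled SVR with a single 12% and does nothing to make the genotype mixes comparable, so following it as written can give a wrong conclusion in either direction. Under the assumed rates, the false-positive risk at 6 to 15 genotype 2/3 patients runs from 0.9–4.7% (8%/20%) to 4.5–23.3% (10%/30%), against a nominal 2.2%.

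The inflation requires both a higher no-effect SVR in genotypes 2/3 and a larger share of them here than in the source. If the rates are equal or the mixes match, genotype introduces no bias. A reader might conclude that genotype mix will produce a positive trial without any drug effect; the documents support only that the plan does not guard against it. The inclusion of relapsers in the benchmark may partly offset the inflation.

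**What to change.** Before results are known, amend Section 7.1 to:

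- state the genotype mix behind the 12%, and the no-effect SVR for non-responders by genotype group (1/4/5 and 2/3) from the historical source;
- test the total SVR count against the value expected for the mix actually enrolled, using the exact sum of two binomials;
- report SVR by genotype stratum.

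If the source gives no usable genotype-specific rates, say so, report SVR by stratum, and show how the conclusion changes over a stated range of null rates.

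No extra visit or measurement is needed, since genotype is already determined at baseline (Appendix 1). The costs are statistical. The critical count will depend on the enrolled mix, historical stratum rates may be imprecise, and the stated 80% power must be given for a range of mixes. With assumed rates of 10%/30% and 10 genotype 2/3 patients of 30, the null is 16.7%, the plan's formula asks for about 32 patients, and the cut-off becomes at least 10 of 30 (upper-tail error 1.6%, power about 71% for a 20-point gain in each stratum). With 8%/20% and the same mix, the null stays at 12%, n at 26.5 and the cut-off at 8, so nothing changes.

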## 2. Rational of the Study

- 50-60% of patients with chronic hepatitis C are not cured by treatment with pegylated IFNα plus ribavirin.
- Retreatment of non-responders of previous (pegylated) IFN $\alpha$  plus ribavirin therapies with pegylated IFN $\alpha$  plus ribavirin results in a sustained response in less than 10% of the patients.
- Extensive analysis of IFNα signaling in cells expressing HCV proteins, in transgenic mice expressing HCV proteins, and in liver biopsies from patients with chronic hepatitis C point to STAT1 methylation as an important posttranslational modification targeted by HCV to inhibit IFNα signaling.
- STAT1 methylation can be increased and IFNα can be improved by adding AdoMet and betaine.
- Analysis of mRNA expression levels of interferon stimulated genes (ISGs) in PBMCs (RNA extracted from whole blood) can be used as a surrogate marker for the activation of the IFN system.

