#### **Inclusion criteria:**

- Male and female between 18 and 65 years.
- Non-responders in previous treatments with IFN $\alpha$  plus ribavirin or pegylated IFN $\alpha$  plus ribavirin.
- Elevated ALT-levels on at least two occasions during  $\geq 6$  months preceding entry.
- Detection of HCV RNA in serum (PCR).
- Compensated liver disease (Child-Pugh A) and a Child-Pugh score ≤5.
- The following minimal hematologic and biochemical criteria:
- Hemoglobin for males and females  $\geq 11g/dl$
- Absolute Neutrophil count ≥1500 cells/mm^3
- Platelets  $> 75'000/\text{mm}^3$
- HBs Ag negative.
- ANA  $\leq 1.320$ , and no evidence for autoimmune hepatitis.
- $\alpha$ -Fetoprotein  $\leq 50 \mu g/l$  (when between upper limit of normal and  $50 \mu g/l$ , ultrasonographical exclusion of hepatocellular carcinoma (HCC) is needed).
- Fasting blood glucose within normal limits, if history of diabetes or hypertension, a pre-therapy ocular examination is indicated.
- TSH within normal limits or adequately controlled.
- Negative urine or blood pregnancy test (for women of childbearing potential) documented within the 2-3 week period prior to the first dose of study drug. Additionally, all fertile males and females must be using effective contraception during treatment and during the 6 months after treatment end. This may include, but is not limited to, using birth control pills, IUDs, condoms, diaphragms, or implants, being surgically sterilized, or being in a post-menopausal state.
- Willingness to give written informed consent and willingness to participate to and comply with the study.

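### Section 7.1 tests a non-responder trial against a 12% rate from a mixed non-responder and relapser cohort and does not fix that rate as the comparator, so the stated 80% power applies only to a true rate of 32%

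*Protocol*

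**What the plan says.** Everything below is in the Protocol.

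- **Population.** Sections 4 and 5 restrict the trial to prior non-responders, 30 in number. The inclusion criterion reads "Non-responders in previous treatments with IFN"α plus ribavirin, or pegylated IFNα plus ribavirin. Relapsers are not included.
- **Null rate.** Section 7.1 cites one published cohort, "385 patients that were non-responders or relapser of a previous treatment with IFN"α plus ribavirin, retreated with peginterferon alfa-2a plus ribavirin. It gives that cohort's sustained response rate as 12% and uses it as π0.
- **The protocol's own figure for non-responders.** Section 2 says that retreating non-responders with pegylated IFNα plus ribavirin "results in a sustained response in less than 10% of the patients". Section 7.1 does not mention this figure.
- **Effect and size.** "We postulate that an improvement of the sustained response rate of 20% or more would be clinically relevant". With π1 = 0.32, two-tailed α of 5% and 80% power, the section concludes: "For this non-responder group, the sample size N = 26.4".
- **Comparator.** "The sustained response rate in this group of patients will be compared to response rates published in other studies (=historical control"). The 12% rate then appears as an example and as the planning value. It is not named as the fixed test value.

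**The concern.** The randomisation provides no control for SVR. Groups A and B differ only in the first week, and both then receive the full four-drug combination (Sections 4, 10.2 and 10.3). The historical rate therefore acts as the control arm. It needs to describe the patients enrolled and to be fixed in advance.

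Section 7.1 falls short on both counts. A cohort that includes relapsers is not this population, and the source cohort had failed IFNα plus ribavirin, whereas this trial also admits failures of pegylated IFNα. The plural wording also leaves room to choose another published rate once the SVR count is known.

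Two things are at stake: whether the stated 80% power applies to a 20-point gain in the patients actually enrolled, and whether the success threshold is settled before the result is seen.

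**Working it through.** **Inputs.** From Section 7.1: π0 = 0.12, π1 = 0.32, two-tailed α = 0.05 (z = 1.96), power 80% (z = 0.84), gain of 20 points. From Section 5: n = 30. From Section 2: non-responder rate below 10%. The protocol gives no value below 10%, so every lower rate used here is an assumption, shown as a range.

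**1. The plan's own figure.** n = [(1.96·√(0.12·0.88) + 0.84·√(0.32·0.68)) / 0.20]² = [(0.637 + 0.392) / 0.20]² = 26.46. The stated 26.4 reproduces, so the arithmetic is not at fault.

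**2. Success rule against 12% at n = 30.** With X binomial(30, p) and an upper tail of at most 0.025:
- P(X ≥ 7 | 0.12) = 0.061, too large.
- P(X ≥ 8 | 0.12) = 0.022, so success needs at least 8/30.

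**3. False-positive risk of that rule if the true no-effect rate is lower.** P(X ≥ 8) is 0.022 at 12%, 0.008 at 10% and 0.002 at 8%. Keeping 12% is therefore conservative.

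**4. Power of that rule.**

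| True SVR rate | Meaning | P(X ≥ 8) |
|---|---|---|
| 32% | 12% + 20 points (the plan) | 0.792 |
| 30% | 10% + 20 points | 0.719 |
| 28% | 8% + 20 points (assumed base) | 0.632 |

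**5. Threshold if the null is lowered (n = 30, upper tail at most 0.025).**

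| Null rate | Minimum successes | Tail |
|---|---|---|
| 12% | 8 | 0.022 |
| 10% | 8 (7 gives 0.0258) | 0.008 |
| 9% (assumed) | 7 | 0.015 |
| 8% (assumed) | 7 | 0.008 |
| 7% (assumed) | 6 | 0.016 |
| 6% (assumed) | 6 | 0.008 |
| 5% (assumed) | 5 | 0.016 |

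**6. Null and alternative lowered together, by the protocol's formula.** With unrounded z values, n is 26.5 for 12% to 32%, 23.7 for 10% to 30%, 22.2 for 9% to 29% and 20.7 for 8% to 28%. All the lower pairs are within the planned 30. Exact power at n = 30 is P(X ≥ 8 | 0.30) = 72% for a 10% null and P(X ≥ 7 | 0.29) = 81% for a 9% null.

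**The case against.** A reader might infer that Sections 2 and 7.1 contradict each other. They do not. A mixed cohort can respond at 12% while its non-responders respond at less than 10%. The fault is using the mixed rate as the benchmark for a non-responder trial.

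A reader might also infer that the trial is too small or prone to a false positive claim. Neither is supported. If 12% is too high for these patients, the false-positive risk falls, and a matched lower null needs fewer patients than the plan already has.

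Four further objections are fair:

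- **Two baselines.** The 63-72% keeps the null at 12% but measures the gain from 8-10%, whereas Section 7.1 measures it from 12%. That is correct as a description of the plan. But the section calls a 20-point improvement clinically relevant, and an improvement is measured from what these patients would otherwise achieve. The figure stands with its assumption stated.
- **Discreteness.** At a 10% null the threshold is 8/30, the same as at 12%. Power is 72% because 7/30 just misses (tail 0.0258); at 7/30 it would be 84%. This stands.
- **Changes of verdict.** It is tempting to say that any result of 5 to 7 responders changes verdict with the benchmark. Under the two figures in the document, 12% and the 10% bound, the threshold is 8/30 both times. A lower threshold needs a null of 5-9%, which Section 2 permits but the protocol never states.
- **Openness of the comparator.** 12% is the only SVR rate given with a source, and it enters the calculation. The comparator is thus only partly open, and the plural may be loose wording. The protocol still does not commit to 12% as the test value.

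The pilot label in Section 4 carries less weight, because Section 3 sets a superiority hypothesis and Section 7.1 claims 5% significance and 80% power.

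**Conclusion.** The point holds in a limited form. Section 7.1 uses a benchmark from a different patient mix and does not fix it as the comparator, although it is the only control for the primary endpoint.

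If 12% is kept, the cost is power: 79% at a true rate of 32%, but 63-72% for a 20-point gain over an assumed non-responder rate of 8-10%. False-positive control is then better than nominal. If a lower published rate were substituted after the data are seen, the threshold would drop to 7/30 for an assumed null of 8-9%, 6/30 for 6-7% or 5/30 for 5%, and that protection would be lost.

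These figures assume all 30 patients are analysed, an exact binomial test and an upper tail of 2.5%. The protocol does not split the 385 patients into non-responders and relapsers, so the non-responder rate behind the 12% cannot be derived from it. This is a clarification worth making before any SVR result is known. It does not invalidate the design or the sample size.

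**What to change.** In Section 7.1, replace the plural comparator with one null rate, fixed before any SVR is known, justified for prior non-responders and reconciled with Section 2. There are two acceptable routes:

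1. **Use a non-responder rate**, with its source, and set π1 = π0 + 0.20. Restate the power at n = 30: for 10%, at least 8/30 and exact power 72%; for 9%, at least 7/30 and 81%. The protocol's own formula needs 23.7 patients at 10% and fewer below that, so 30 stands.
2. **Keep 12%**, say that it is deliberately conservative because the source cohort includes relapsers, and restate the power as about 63-72% for a 20-point gain over an assumed 8-10%.

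Either route is a wording change. The cost is that the stated power may look less favourable. No extra patients are needed.

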## 7.2. Secondary Endpoints:

For secondary endpoint 1, virological response after 12 weeks will be assessed, and compared to a historical control, where an early virological response rates of 28% was found (22).

For secondary endpoint 2, RNA samples extracted from whole blood at baseline, and 24, 48 and 96 hours after the first injection of PegIntron will be analyzed by real-time RT-PCR (Taqman) for the concentrations of ISGs including IP-10, ISG15, ISG54, PKR and 2'5'OAS. The results from groups A and B will be compared using the Wilcoxon rank test.

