#### 8. Randomization

After inclusion in the study, the patients are randomly assigned to Group A or Group B. The randomization will be done in two separate groups for genotype 1 and 4 and for genotypes 2 and 3, respectively. In each group, a list with a randomized sequence of A's and B's in blocks of 10 will be used to sequentially assign the patients into groups A or B (appendix 4).

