### 10.3. Treatment Group B Patients:

Patients will receive one week of treatment with PegIntron and Rebetol, followed by a combination treatment with PegIntron, Rebetol, AdoMet and betaine. The dosages are identical to group A.

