## Appendix 1a: Schedule of Assessments in group A

	Baseline	At the end of 1 week of AdoMet- Betaine (pre-)	During full combination treatment after 1, 2, 4 days, 1, 2, 4, 6, 8, 12 weeks, thereafter every 6 weeks	Follow-up 6 months after end of treatment
		treatment	until end of treatment	
Medical history	X			
Adverse Events / Tolerability	X	X	X	X
Physical Exam / Vital Signs	X	X	X	X
Concomitant Medication	X	X	X	X
Hematology	X	X	X	X
Blood chemistry	X	X	X	X
Quick / INR	X			
AFP	X			
ANA	X			
TSH	X		X (a)	X
HBs Ag, HAV- IgM, HIV-test	X			
Liver biopsy	X (b)			
Urinanalysis	X			
Pregnancy Test	X		X (c)	X
HCV genotype	X			
HCV RNA	X	X	X (d)	X
quantitative				
Isolation of	X	X	X (e)	
leucocytes and				
asservation of				
serum				

- (a) only at week 12, 24 and 48
- (b) if not done within 12 months prior to study entry
- (c) every 4 weeks
- (d) at day 1, 2, 4, week 1, 2, 4, 8, 12, 24, 48
- (e) at day 1, 2, 4 (24hours, 48hours, 96hours), week 1 after first injection of PegIntron, then weeks 2, 4, 6, 8, 12, 24, 48

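### The A-versus-B comparison of ISG induction ignores the genotype strata used in randomisation and leaves the pre-injection reference sample in group A undefined

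*Protocol*

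**What the plan says.** Secondary endpoint 2 (protocol section 6) is "Cmax and AUC of mRNA induction of IFN stimulated genes over 96 hours after first injection of PegIntron". Section 7.2 names the samples as "RNA samples extracted from whole blood at baseline, and 24, 48 and 96 hours after the first injection of PegIntron", lists "concentrations of ISGs including IP-10, ISG15, ISG54, PKR and 2'5'OAS", and gives the test: "The results from groups A and B will be compared using the Wilcoxon rank test". It mentions no strata and does not say which sample induction is measured from.

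On allocation, section 8 says: "The randomization will be done in two separate groups for genotype 1 and 4 and for genotypes 2 and 3, respectively". Section 4 says the same.

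The groups differ in what precedes the first PegIntron injection. Group A, in section 4, "will be treated during the first week with AdoMet and Betaine, followed by a combination treatment of PegIntron, Rebetol, AdoMet and Betaine". For group B, section 10.3 says: "Patients will receive one week of treatment with PegIntron and Rebetol, followed by a combination treatment with PegIntron, Rebetol, AdoMet and betaine". Appendix 1a gives group A two visits before PegIntron: Baseline, and a second column that begins "At the end of 1 week of AdoMet- Betaine (pre". The row for leucocyte isolation and stored serum is marked at both. Appendix 1b gives group B one pre-injection visit, Baseline.

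**The concern.** The primary endpoint and secondary endpoint 1 are set against historical controls. The ISG comparison is the only place where the plan uses its randomisation, and section 4 says the two groups exist to test the marker. Two features of section 7.2 weaken it.

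First, a test that ignores the randomisation strata leaves any genotype difference in the noise. With about 15 patients per group there is little power to spare.

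Second, an AUC from 0 to 96 hours after injection needs a value at time zero. In group B, baseline serves. In group A, the only pre-injection value that section 7.2 names appears to lie about a week and one treatment before time zero. The rationale in sections 1 and 2 is that AdoMet and betaine improve interferon signalling, so a change in basal ISG level during that week cannot be assumed to be zero.

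**Working it through.** **Inputs from the protocol.** 30 patients (section 5), half to each group (section 4), so 15 and 15; two genotype strata (section 8); Wilcoxon test (section 7.2). Section 7.2 states no power or significance level. The only computed figure in the plan is the sample size for the primary endpoint, which reproduces: ((1.96·√0.1056 + 0.84·√0.2176)/0.20)² = 26.46, against 26.4 printed. It has no bearing on this point.

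**Assumed, because the protocol gives no figure.** Two-sided 5% level; normally distributed scores with SD 1; a treatment effect of 1 SD; strata of 20 and 10, or of 22 and 8, each split equally between A and B; genotype shifts from 0 to 2 SD; no missing samples.

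**Step 1: the two tests.**
- Unstratified: Z = (W − m(n+1)/2)/√(m(n−m)(n+1)/12). With m = 15 and n = 30, the null mean is 232.5 and the null variance is 15·15·31/12 = 581.25.
- Van Elteren: Z = Σ[(W_k − m_k(n_k+1)/2)/(n_k+1)] / √Σ[m_k(n_k−m_k)/(12(n_k+1))]. With strata of 20 and 10, the variance is 100/252 + 25/132 = 0.397 + 0.189 = 0.586.

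The variance 581.25 allows for chance imbalance of genotype between the groups, which stratified randomisation largely removes. When genotype matters, that variance is too large and the test is conservative.

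**Step 2: simulation, strata 20/10, 40,000 trials per setting.**

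| Genotype shift (SD) | Type I error, unstratified | Type I error, stratified | Power, unstratified | Power, stratified |
|---|---|---|---|---|
| 0 | 4.9% | 4.9% | 72.6% | 70.6% |
| 0.5 | 4.3% | 4.7% | 70.9% | 70.8% |
| 1 | 3.2% | 4.9% | 64.8% | 71.1% |
| 1.5 | 1.6% | 4.8% | 54.5% | 70.9% |
| 2 | 0.8% | 4.8% | 42.6% | 71.1% |

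With strata of 22/8, power (unstratified vs stratified) is about 72 vs 70% at no shift, 67 vs 72% at 1 SD and 49 vs 70% at 2 SD.

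Loss from not stratifying: about 0 points at 0.5 SD; 72 − 67 = 5 to 71.1 − 64.8 = 6 points at 1 SD; 70 − 49 = 21 to 71.1 − 42.6 = 28 points at 2 SD. Cost of stratifying with no genotype effect: 72.6 − 70.6 = 2 points here, and 1 to 2 in the 22/8 runs.

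**Step 3: what each reference sample measures.** Suppose, for illustration, that AdoMet/betaine alone multiplies basal ISG mRNA by 1.3.
- If post-injection levels rise by the same factor, so that the fold response to PegIntron is unchanged, group A's fold-induction is 30% higher from the pre-treatment baseline and unchanged from the last pre-injection sample.
- If post-injection levels do not change, group A's fold-induction is unchanged from the pre-treatment baseline and 1 − 1/1.3 = 23% lower from the last pre-injection sample.

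The two references answer different questions, and neither result can be interpreted without the other.

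**Step 4: size of the ambiguity.** Take the pre-treatment baseline, with AdoMet/betaine shifting ISG level by 0.25, 0.5 or 1 SD and the response to PegIntron unchanged. The A-B test (15 vs 15) is then significant in 10%, 25% and 73% of simulated trials, against 5% with no shift. These are real effects of the sequence, but they are not a stronger response to PegIntron.

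**The case against.** **The comparison might be called confounded.** It is not. If baseline means the Appendix 1a column, it is untreated in both groups and comparable by randomisation. A minus B from it validly estimates the effect of AdoMet/betaine plus PegIntron/Rebetol against PegIntron/Rebetol alone, which fits the study hypothesis. What remains is a limit on interpretation: the endpoint speaks of induction after the injection, and this contrast does not isolate that.

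**The text is ambiguous, not wrong.** Section 7.2 speaks of concentrations and does not say that baseline is divided out. That baseline means the Appendix 1a column is an inference, though the natural one. This stands, and it is why the point concerns an undefined reference. Changing the reference is no plain correction either, since group A's value would then be on treatment and group B's untreated (step 3). Both comparisons should therefore be reported.

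**Stratification could be left to an analysis plan, and no genotype effect is documented.** Both are fair and limit the weight of the point. Still, the protocol names its test and its strata and does not connect them, and the possible loss far exceeds the cost of stratifying.

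**A reader might infer that ignoring strata produces false positives.** The reverse holds: type I error falls to about 1% at a 2 SD shift.

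**A reader might also object to multiplicity**, since five named genes and two measures could give ten tests. These are secondary marker analyses in a 30-patient pilot with no confirmatory claim, and rules for multiple tests commonly sit in an analysis plan. The documents do not support a finding there.

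**Conclusion.** The point holds in two limited parts.

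1. The stated test does not follow the randomisation. The harm is a conditional loss of power, in the sizes shown in step 2. It is neither bias nor excess error. How much is lost in this trial is unknown, because it depends on a genotype effect and stratum sizes that the protocol does not give.
2. The reference sample for induction is not defined. On the natural reading, group A's reference precedes the lead-in week, so the result describes the whole sequence and cannot separate a basal shift from a changed response to PegIntron. The figures in steps 3 and 4 are illustrative; the protocol gives none for a basal shift.

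The second part should be settled in the protocol, because it decides which blood samples must exist. The endpoint needs whole-blood RNA, while the Appendix 1a row for the end-of-pretreatment visit refers to leucocyte isolation and stored serum. RNA not collected at that visit cannot be recovered by a later analysis plan.

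**What to change.** In section 7.2:

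- Replace the test by the Wilcoxon test stratified by genotype group (van Elteren), with the stratum taken as the list from which the patient was randomised. Say where a genotype 5 patient belongs: section 10.2 mentions that genotype, but neither list does.
- State that induction in both groups is measured from the last sample before the first PegIntron injection: the end-of-pretreatment visit in group A, Baseline in group B.
- Report two results beside it: group A's change over the lead-in week, and the A-B comparison from the pre-treatment baseline.

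In Appendix 1a, confirm that whole-blood RNA is taken at the end-of-pretreatment visit.

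The cost is wording, 1 to 2 points of power if genotype has no effect, and, if not already planned, one RNA sample per group A patient at a visit that is already scheduled. No treatment rule changes.
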